### 9.0 TREATMENT/INTERVENTION PLAN

### 9.1. Mocetinostat administration

Mocetinostat will be administered on a three times per week dosing schedule. There will be no breaks between dosing cycles. Mocetinostat will be initiated at 70 mg orally three times per week for cycle 1. The dose will be increased to 90 mg orally three times per week

The following general guidelines should be followed for mocetinostat administration:

- Patients should be instructed to take the dose of mocetinostat three times a week in the morning, at approximately the same time each day
- Mocetinostat should be taken at least 1 hour following a light breakfast.
- Patients should not eat for 2 hours after the administration of each mocetinostat dose.
- Mocetinostat should be taken with a low pH beverage (Table 9-1). Patients should swallow the capsules as a whole and not chew them.
- If vomiting occurs during the course of treatment, no re-dosing of the patient is allowed before the next scheduled dose. The occurrence and frequency of any vomiting during a treatment cycle must be noted in the adverse events section of CRDB.

Table 9-1. List of low pH beverages	
Coca cola, diet cola	Lime juice
Cranberry juice	Lemon juice
Hawaiian Fruit Punch	Orange juice
[name]	Orange soda
Gatorade	Pepsi cola, +/- caffeine

### 9.2. Mocetinostat dose modification

Patients will be initiated at 70 mg mocetinostat three times per week for 1 cycle and observed for toxicities. If there are no grade 3 or higher drug related toxicities, the dose will be increased to 90 mg starting cycle 2 if thre are no grade 3 or higher treatment related toxicities.

Mocetinostat dose reduction will be administered at 20 mg below the current dose. For each patient, a maximum of 3 dose reduction (minimum dose of 35 mg three times per week) will be allowed after which the patient will be discontinued from treatment with mocetinostat (Table 9-2). Once a dose has been reduced during a treatment cycle, re-escalation will not be permitted during any subsequent cycle. If the administration of mocetinostat is interrupted for reasons other than toxicity, then treatment with the study drug may be resumed at the same dose. The same applies if the patient experienced an unacceptable toxicity not specifically described in Table 3-3 or Section 9.3, provided this toxicity resolved to  $\leq$  CTCAE grade 1, unless otherwise specified.

If treatment with the study drug is withheld for  $\geq$ 21 consecutive days, then study drug must be permanently discontinued. Patients who permanently discontinue the study drug should have followup for 30 days after discontinuation of all study treatment or resolution of the AE to  $\leq$  grade 1, whichever occurs first, that includes all study assessments appropriate to monitor the event.

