# 1.0 PROTOCOL SUMMARY AND/OR SCHEMA

**Title:** An Open-Label Phase II Study of Mocetinostat in Selected Patients with Mutations of Acetyltransferase Genes in Relapsed and Refractory Diffuse Large B-Cell Lymphoma and Follicular Lymphoma

**Objectives:** The purpose of this trial is to determine the therapeutic efficacy of mocetinostat in selected patients with CREBBP/EP300 alterations in relapsed and refractory DLBCL and FL.

**Patient Population:** Patients with histologically confirmed relapsed or refractory diffuse large B cell lymphoma and follicular lymphoma with mutations of CREBBP or EP300.

**Study Design:** This is an open label phase II study in patients with relapsed and refractory NHL in 2 histologic subgroups: diffuse large B cell lymphoma and follicular lymphoma. Patients with mutations of CREBBP and/or EP300 will be eligible for the trial. Eligible patients will be be treated by mocetinostat and monitored for overall response, event free survival, and duration of response.

**Treatment Plan:** Patients who harbor mutations for CREBBP and/or EP300 will be started on mocetinostat 70 mg orally three times per week on a 28 day schedule in cycle 1. The dose will be escalated in cycle 2 to 90 mg orally three times per week on a 28 day schedule if there are no grade 3 or higher drug related toxicities. Therapy will continue until disease progression, intolerable toxicities or death.

**Time to Completion:** We anticipate that this study will enroll 10 patients in each cohort of follicular lymphoma and diffuse large B cell lymphoma. If 2 or more patients in each cohort show a response, we will enroll an additional 15 patients in that cohort for the second stage of the trial. Assuming a dropout rate of 10%, we plan to enroll 56 patients total, 28 patients in each cohort over 48 months.

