# 3.0 BACKGROUND AND RATIONALE

### 3.1 Rationale

This is a single center, open label, single arm single step phase II study of mocetinostat in patients with relapsed and refractory DLBCL and FL harboring mutations in CREBBP and EP300 (Figure 2-1). The integrated assessment of CREBBP and EP300 mutations were chosen based on preclinical data suggesting patients harboring CREBBP or EP300 mutations may be more sensitive to HDAC inhibition[1]. The purpose of this study is to determine the therapeutic efficacy of mocetinostat in selected patients with CREBBP/EP300 alterations in relapsed and refractory DLBCL and FL. Approximately 30% of patients with DLBCL and FL harbor inactivating mutations in acetyltransferase genes which may make their disease more susceptible to HDAC inhibition. Mocetinostat has been previously shown to elicit modest responses of 15-17% in unselected DLBCL and FL patients[2]. Selection for populations of DLBCL and FL patients with increased sensitivity to HDAC inhibition may identify a population of patients with a heightened response to HDAC therapy. The starting dose for mocetinostat for this study is based on the results of the prior phase II clinical trial assessing mocetinostat in DLBCL and FL. The starting dose will be 70 mg orally three times a week on a 28 day schedule on cycle 1 followed by dose increase to 90 mg orally three times a week on a 28 day schedule if there are no grade 3 or higher drug related toxicities. Dose reductions will be determined based on side effect profile.

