# 4.1 OVERVIEW OF STUDY DESIGN/INTERVENTION

# 4.2 Design

This is a phase II single center single stage clinical trial evaluating the efficacy of mocetinostat in a population of patients with DLBCL or FL with inactivating mutations of acetyltransferase genes CREBBP and/or EP300.

A pre-screening evaluation of archival tumor biopsies from current relapse or fresh tumor biopsies is required for CREBBP and EP300 analysis. Potential eligible patients will be asked to sign a "Molecular Pre-screening Informed Consent." The patient's archival tumor from the current relapse or a fresh tumor biopsy will be obtained. This will ensure that the CREBBP/EP300 molecular status of the tumor is known when the potential patient is screened for enrollment into the study.

Twenty-eight patients will be enrolled in each cohort with an anticipated analysis of 25 patients in each cohort for a total of 50 evaluable patients. Patients will be started on mocetinostat and monitored for response by physican exam and imaging. Treatment will be organized into cycles of 28 days in all cohorts and patients will receive mocetinostat orally three times a week at 70 mg for cycle one and increased to 90 mg for cycle 2 onwards barring any grade 3 or higher drug related toxicities. Treatment will continue until disease progression, intolerable toxicity, withdrawal of consent, or until other criteria for discontinuation are met, whichever comes first.

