#### 9.3. Guidelines for dose reduction based on toxicities

#### 9.3.1. Management on non-hematologic toxicities

In the case of drug-associated grade 3 non-hematologic toxicities experienced by the subject, hold treatment (one or both drugs if applicable) until toxicity is resolved to  $\leq$  grade 1 or to baseline value. If further treatment is desired, treatment should then be resumed at the next lower dose level for the applicable drug(s). If the toxicity can be managed by routine supportive care, such as anti-emetics or electrolyte supplementation, then a dose reduction is not required. If there is no recovery within 21 day the subject will go off protocol treatment, unless the clinical investigator in discussion with MethylGene/Mirati deems that it is in the best interest of the subject to resume treatment. If grade 3 non-hematologic toxicity recurs following the first dose reduction, a second dose reduction of one dose level may be implemented following recovery to  $\leq$  grade 1 or to baseline. However if grade 3 non-hematologic toxicity again recurs, then the subject should be removed from protocol therapy. Subjects who experience grade 4 non-hematologic toxicities should have study treatment discontinued, unless the Investigator and the sponsor agree that the subject is benefiting from study treatment, in which case, treatment may be resumed at a lower dose level as described above following recovery. Dose reductions for lower-grade toxicities may also be implemented based on Investigator discretion; however the sponsor should be notified of such an event (Table 9-3).

Table 9-3. Dose Modifications – Non-Hematologic Drug Related Toxicities 					
Occurrence	Toxicity	Treatment Delay	Dose Modification		
1st Occurrence	< Grade 3	May be implemented based on Investigator and subject			
		discretion; Sponsor should be no	otified		
	Grade 3	Hold until ≤ Grade 1 or return	Then, resume at next lower		
		to baseline	dose level		
	Grade 3 toxicity manageable	Hold until ≤ Grade 1 or return	Not required		
	with routine supportive care	to baseline			
	Grade 4		Remove from Therapy		
2nd Occurrence	Grade 3	Hold until ≤ Grade 1 or return	Then, resume at next lower		
		to baseline	dose level (e.g., 2nd dose		
			reduction)		
3rd Occurrence	Grade 3		Remove from Therapy 		

1For pericardial toxicity, see Section 6.2.2.

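### The cycle 2 step to 90 mg is gated only on grade 3 or higher drug-related toxicity, so a patient under weekly ECHO watch for a new small pericardial effusion qualifies for it, and no text provides for staying at 70 mg

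*Combined protocol and SAP*

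**What the plan says.** Section 9.2 states the rule: "If there are no grade 3 or higher drug related toxicities, the dose will be increased to 90 mg starting cycle 2". The summary in section 1.0 says "The dose will be escalated in cycle 2 to 90 mg orally three times per week on a 28 day schedule", subject to the same condition, and section 4.3 repeats this. Section 3.1 allows the increase "if there are no grade 3 or higher drug related toxicities", and section 4.2 has the dose "increased to 90 mg for cycle 2 onwards barring any grade 3 or higher drug related toxicities". Section 9.1 states the step with no condition: "The dose will be increased to 90 mg orally three times per week".

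Section 9.3.4 and Table 9-4 deal with effusions by size.
- **Minimal or trivial:** the patient stays on drug with a short period of closer monitoring.
- **Small and new on study:** weekly ECHO and ECG for the first month, or until regression if sooner. The drug continues unless the effusion progresses, with discretion left to the investigator.
- **Moderate, large, or any hemodynamic compromise:** the patient comes off treatment.

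None of these entries mentions the step to 90 mg.

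Table 10-1 and section 10.4 schedule ECHOs on cycle 1 day 15, cycle 2 day 1 (pre-dose) and cycle 2 day 15. From cycle 3 they are done as clinically indicated.

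On lower doses, section 9.2 says "Mocetinostat dose reduction will be administered at 20 mg below the current dose" and "Once a dose has been reduced during a treatment cycle, re-escalation will not be permitted during any subsequent cycle". Section 9.3.1 adds "Dose reductions for lower-grade toxicities may also be implemented based on Investigator discretion".

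**The concern.** The escalation rule and the pericardial rule were written separately, and they meet on cycle 2 day 1. The plan treats a new small effusion as serious enough for a month of weekly imaging. Yet the dose rises during that month unless the event is grade 3 or higher and drug-related.

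Section 3.2.8 reports that enrolment in the earlier DLBCL and FL trial was interrupted to investigate pericardial events and resumed at 70 mg. Section 6.3 excludes anyone with a present or past effusion. A patient who develops a small effusion at 70 mg is in a state that would have barred entry, and qualifies for a higher dose. The mildest precaution, staying at 70 mg until the effusion clears, is not written anywhere. An investigator who takes it departs from a rule worded as mandatory.

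What is at stake is dosing safety for a few patients. The Simon two-stage figures in section 14.0 do not depend on it.

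**Working it through.** **Timing on the 28-day cycle.** Cycle 1 day 15 is study day 15, cycle 2 day 1 is day 29 and cycle 2 day 15 is day 43. The watch month is taken as 28 days.
- Small effusion found on day 15: the watch runs to 15 + 28 = day 43. The step on day 29 falls 14 days into it. Weekly rechecks fall on about days 22 and 29, and both can be read before the first 90 mg dose.
- Small effusion first seen on day 29: the watch starts on the day of the step and runs to 29 + 28 = day 57, which is cycle 3 day 1. There is no recheck before the step.

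**Size of the step.** 90/70 = 1.286, an increase of 28.6%.

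**Written ways to avoid or leave 90 mg.**
- Stop the drug (9.3.4; 13.1).
- Withhold it, if the row of Table 9-3 for toxicity below grade 3 covers pericardial events. Section 9.2 requires permanent discontinuation once 21 or more consecutive days are withheld, so a hold for the full watch month does not fit.
- Reduce before the step: 70 - 20 = 50 mg, which is 50/90 = 56% of the target dose, with re-escalation barred.
- Reduce after the step: 90 - 20 = 70 mg, also with re-escalation barred. This reaches 70 mg only after 90 mg has been started.

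None of these is simply staying at 70 mg.

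**How many patients.** The documents give no rate for new small effusions in cycle 1. The nearest proxy is any non-serious pericardial finding, multiplied by an assumed cycle 1 share.

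Rates:
- NHL patients (Table 3-7): 8 findings less 3 SAEs gives 5 of 80 = 6.25%.
- Prospective ECHO monitoring (Table 3-5; tumor mix not stated): 13 of 35 = 37.1%.

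Cycle 1 share: section 3.2.8 gives 54.8% for pericardial AEs and 73.7% for SAEs, and 73.7% is 14/19. With denominators of 45 or less, 54.8% fits only 17/31 or 23/42.
- If the AEs include the SAEs: (17 - 14)/(31 - 19) = 3/12 = 25%, or (23 - 14)/(42 - 19) = 9/23 = 39%.
- If they do not: 54.8%.

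Results are expected counts at shares of 25%, 39% and 54.8%:

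| Source | Enrolled | All cycles | In cycle 1 |
|---|---|---|---|
| NHL, 5/80 | 56 | 3.5 | 0.9, 1.4, 1.9 |
| Prospective ECHO, 13/35 | 56 | 20.8 | 5.2, 8.1, 11.4 |
| NHL, 5/80 | 20 | 1.25 | 0.3, 0.5, 0.7 |
| Prospective ECHO, 13/35 | 20 | 7.4 | 1.9, 2.9, 4.1 |

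The rows with 20 patients apply if both cohorts stop after stage 1.

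These are not upper limits. The exact 95% upper bounds on the rates are 14.0% (5/80) and 55.1% (13/35). For 56 patients they give 56 x 0.140 x 0.25 to 0.548 = 2.0 to 4.3, and 56 x 0.551 x 0.25 to 0.548 = 7.7 to 16.9.

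Other features pull the number that matters downward. The counts include minimal or trivial effusions and patients who never reach cycle 2. Many earlier patients started at 110 mg or had 85 mg. Patients with a prior effusion are now excluded.

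**The case against.** The strongest reply is that the protocol did consider small effusions and chose a rule: keep the drug, image weekly, remove the patient at moderate size or above. Section 3.2.8 supports that choice, since nearly all the non-serious findings were minimal, trivial or small and needed no intervention. It also names 90 mg as the MTD, after describing the pericardial pause. This stands, and it keeps the point minor. It does not answer it, because the chosen rule covers continuing the drug and is silent on raising the dose.

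A reader might infer that the investigator is forced to give 90 mg. The documents do not support that. The drug can be stopped, and sections 9.3.1 and Table 9-3 arguably allow delay or reduction below grade 3. The table's layout is uncertain, and its footnote sends pericardial toxicity to a Section 6.2.2 that does not exist. Section 9.3.4 is plainly meant, so the footnote is a clerical slip and not evidence of a design fault.

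A reader might also infer that escalation always happens blind. That holds only for an effusion first seen on cycle 2 day 1.

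Finally, a bare deferral could weaken monitoring. ECHOs are scheduled only through cycle 2 day 15, so a step moved to cycle 3 would have no scheduled ECHO at 90 mg. This objection is correct, and the change proposed here allows for it.

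**Conclusion.** The gap holds as a minor dosing-safety point worth considering. Followed as written, the plan makes a patient with a new small effusion eligible for a 28.6% increase during the watch for that effusion, and it offers no hold at 70 mg.

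This rests on one assumption: that the effusion is below grade 3. The documents do not map effusion size to CTCAE grade, and a drug-related grade 3 event would block the step.

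The number affected is small and may be near zero. The expected counts of about 1 to 2 or 5 to 11 of 56 describe a broader group, and their cycle 1 share is itself an assumption.

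It would go too far to conclude that 90 mg is known to worsen effusions. The documents give no dose-response data for pericardial events, so the added risk cannot be stated. The response endpoint is little affected.

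**What to change.** Add to section 9.2, and mirror in sections 1.0, 3.1, 4.2, 4.3 and 9.1:

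> The dose is not increased to 90 mg while a new small pericardial effusion is present on the pre-dose cycle 2 day 1 ECHO; the patient stays at 70 mg and may go to 90 mg at a later cycle once ECHO shows the effusion has regressed to minimal or none. The ECHOs tied to the step (pre-dose day 1 and day 15) move to the first 90 mg cycle.

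Minimal or trivial effusions do not block the step. A patient whose small effusion persists stays at 70 mg. Staying at 70 mg is not a reduction, so the bar on re-escalation does not apply.

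The cost is that a few patients reach 90 mg a cycle or more late, or not at all. One or two ECHOs per such patient fall in a later cycle, where they are already allowed as clinically indicated. The decision itself uses an ECHO that is already scheduled.

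As a separate clerical correction, point the Table 9-3 footnote to Section 9.3.4.

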#### Table 9-2. Dose modifications for mocetinostat

Mocetinostat dose levels and reductions*	
Starting dose 0	70 mg three times per week
Dose level 0	70 mg three times per week
Dose level –1	50 mg three times per week
Dose level –2	35 mg three times per week**

\*Dose reduction should be based on the worst preceding toxicity

\*\*Dose reduction below 35 mg 3x/week is not allowed. If a dose reduction below 35 mg 3x/week is required, the patient should be permanently discontinued from mocetinostat.

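### Section 9.2's fixed 20 mg reduction cannot reach the 35 mg level in Table 9-2, and its 21-day stopping rule, like that in Section 13.1, lacks the exception that Section 9.3.1 allows

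*Combined protocol and SAP*

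**What the plan says.** **Dose step.** Section 9.2 starts patients at 70 mg three times a week and raises the dose to 90 mg from cycle 2 if no drug-related toxicity of grade 3 or worse has occurred. For reductions it says "Mocetinostat dose reduction will be administered at 20 mg below the current dose". The following sentence says that "a maximum of 3 dose reduction (minimum dose of 35 mg three times per week) will be allowed" and refers to Table 9-2. That table lists 70 mg as the starting dose and dose level 0, 50 mg as level -1, and "35 mg three times per week" as level -2. It has no 90 mg row. Its footnote adds: "If a dose reduction below 35 mg 3x/week is required, the patient should be permanently discontinued from mocetinostat".

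Section 9.3.1 and Table 9-3 work in dose levels, not milligrams. After a first drug-related grade 3 non-hematologic toxicity the patient resumes one level down. On recurrence, "a second dose reduction of one dose level may be implemented following recovery". After that, "However if grade 3 non-hematologic toxicity again recurs, then the subject should be removed from protocol therapy", although Table 9-3 footnote 2 lets the investigator and sponsor agree to continue one level lower. Section 9.3.1 also says "Dose reductions for lower-grade toxicities may also be implemented based on Investigator discretion", without giving the size of the step.

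**Hold.** Section 9.2 makes discontinuation permanent once drug has been withheld for 21 or more consecutive days. Section 13.1 lists an interruption of more than 21 days among the events that require stopping. Neither states an exception. Section 9.3.1, for non-hematologic toxicity, takes the patient off treatment if recovery has not occurred within 21 days, but allows resumption if the investigator, in discussion with the drug supplier, judges it best for the patient.

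**The concern.** Two pairs of dosing rules give different instructions for the same patient. At 50 mg, the 20 mg rule points below the permitted minimum and so to stopping, while Table 9-2 and the dose-level rule of Section 9.3.1 point to 35 mg. After a long hold for non-hematologic toxicity, Sections 9.2 and 13.1 say stop, while Section 9.3.1 may let the patient continue. A site that follows one section departs from another.

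At stake is who remains on drug. Section 14.0 tabulates adverse events requiring discontinuation separately, so that safety summary would depend in part on which section was followed.

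**Working it through.** **Dose step.** Inputs: starting doses of 70 and 90 mg, a 20 mg step, a 35 mg floor and a maximum of three reductions (Section 9.2); levels 70, 50 and 35 mg (Table 9-2); a limit of two reductions for recurrent grade 3 non-hematologic toxicity (Section 9.3.1, Table 9-3).

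Literal rule, new dose = current dose - 20 mg:
- From 90 mg: 90 - 20 = 70; 70 - 20 = 50; 50 - 20 = 30, below 35. Two usable reductions.
- From 70 mg: 70 - 20 = 50; 50 - 20 = 30, below 35. One usable reduction.

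The stated maximum of three and the stated 35 mg minimum are therefore not reproduced from either starting dose.

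Table 9-2 levels with 90 mg placed on top:
- 90, 70, 50, 35 mg: steps of 20, 20 and 15 mg. Three reductions from 90 mg, two from 70 mg.

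This does reproduce the maximum of three. The two readings agree on 90 to 70 and on 70 to 50. They part only at 50 mg, where the last step is 15/50 = 30% in the table and 20/50 = 40% under the rule.

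With the Table 9-3 limit of two applied (before footnote 2), the usable reductions are the smaller of that limit and the count above:

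| Situation | 20 mg rule | Table 9-2 levels |
|---|---|---|
| Grade 3 non-hematologic, reductions start at 90 mg | min(2, 2) = 2 | min(3, 2) = 2 |
| Grade 3 non-hematologic, reductions start at 70 mg | min(1, 2) = 1 | min(2, 2) = 2 |
| Discretionary lower-grade reductions, from 90 mg | 2 | 3 |
| Discretionary lower-grade reductions, from 70 mg | 1 | 2 |

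The second row is the clearest case. A drug-related grade 3 toxicity in cycle 1 blocks escalation, the first reduction takes the patient from 70 to 50 mg, and the second reduction that Table 9-3 permits is exactly the disputed step. In the first row there is no difference unless footnote 2 is used after a third occurrence.

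Capsule strengths do not explain the discrepancy. With the 10 mg and 25 mg capsules of Section 5.3, 35 = 25 + 10 and 30 = 3 x 10 can both be made.

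**Hold.** No arithmetic applies; the rules side by side, for a hold due to non-hematologic toxicity:

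| Length of hold | Section 9.2 | Section 13.1 | Section 9.3.1 |
|---|---|---|---|
| Under 21 days | may continue | may continue | may resume after recovery |
| Exactly 21 days | must stop | no stop required | may resume if recovered within the 21 days |
| Over 21 days | must stop | must stop | stop, unless investigator and supplier discussion supports resuming |

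The difference in threshold matters only at exactly 21 days. The larger conflict is in the last row: a mandatory stop in two sections against a discretionary resumption in the third.

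**The case against.** The strongest reply on the dose step is that Sections 9.2 and 9.3.1 and the two tables should be read together. Three reductions from 90 mg that end at 35 mg can only be 70, 50, 35. Table 9-2 names 35 mg as a level, and its footnote stops drug only when a dose below 35 mg is needed, which is not so while a 35 mg level is available. On that reading the 20 mg sentence merely omits the shorter last step. This stands as to intent: 35 mg was almost certainly meant. It does not remove the conflict, because Section 9.2 nowhere says that the last step is cut short at the floor.

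On the hold, a reader may say that the specific rule of Section 9.3.1 overrides the general one. That is reasonable, but the documents state no such order of precedence, and Sections 9.2 and 13.1 are worded as mandatory. The proviso in Section 9.2 for cases specified otherwise ends a different sentence, about resuming at the same dose, and does not reach the 21-day rule. It is right that the exception is narrow: it covers only non-hematologic toxicity.

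A reader might infer that hematologic toxicity is also caught by the dose-step conflict, since Section 10.3 anticipates dose modifications for it. The documents do not settle this. Section 9.2 lets toxicities not described in Table 3-3 or Section 9.3 resume at the same dose once resolved to grade 1 or better. Section 9.3 has no hematologic rule, and Table 3-3 does not appear in the text reviewed. No count is offered for that case.

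**Conclusion.** Both rules are wrong as written. They are internal inconsistencies of minor severity. The dose-step conflict is confined to patients at 50 mg. It costs one reduction in those who start reducing from 70 mg, or in those with discretionary lower-grade reductions; for grade 3 non-hematologic toxicity starting from 90 mg it makes no difference unless footnote 2 is used. The hold conflict is confined to non-hematologic toxicity, mainly where it is unresolved after 21 days. The documents do not say how many patients would reach either point, so no frequency is claimed.

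A reader might infer that the primary analysis is compromised. The documents do not support that. One documented CR or PR before relapse or progression is enough (Section 12.3), imaging continues after stopping for toxicity (Section 13.2.2), and the Simon stage sizes and decision limits in Section 14.0 do not depend on these rules. Nor is it right to say that there can be no effect at all: a patient taken off drug before responding might have responded had dosing continued. The design and the assessability of response are unchanged; an individual outcome could differ.

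**What to change.** 1. In Section 9.2, replace the 20 mg sentence with *reduce by one dose level per Table 9-2*. Add a 90 mg row so that the table reads 90, 70, 50, 35 mg. State that the maximum of three reductions is subject to the Table 9-3 limit of two for recurrent grade 3 non-hematologic toxicity unless footnote 2 applies.
2. Use one threshold, 21 or more consecutive days, in Sections 9.2 and 13.1. Then either add *except as provided in Section 9.3.1* to both, or delete the exception from Section 9.3.1. The first keeps clinical discretion and the second is the more cautious; the choice is the sponsor's, but one rule should hold throughout.

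The cost is amendment wording, with no added patients or visits. All four doses can be made from the capsules already supplied (35 = 25 + 10; 50 = 2 x 25; 70 = 2 x 25 + 2 x 10; 90 = 2 x 25 + 4 x 10). Under item 1 some patients would continue at 35 mg instead of stopping, which Table 9-2 already provides for. Deleting the exception under item 2 would remove the option to resume in a patient thought to be benefiting.

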In addition to Phase I studies, the safety profile of mocetinostat has been evaluated as a single agent in Phase II studies. Four Phase II studies have evaluated mocetinostat as a monotherapy in the following populations: 1) Elderly, previously untreated patients with AML or MDS or adults with relapsed/refractory AML or high-risk MDS; 2) Patients with relapsed or refractory NHL; 3) Patients with refractory CLL; and 4) Patients with relapsed or refractory HL. The safety profile of mocetinostat has also been investigated in combination with other anticancer agents in Phase I/II and Phase II studies. Mocetinostat has been evaluated with Vidaza® (azacitidine) in patients with MDS, AML, HL, or NHL, with Gemzar® (gemcitabine) in patients with refractory solid tumors or pancreatic cancer, and with docetaxel in patients with solid malignancies. As of April 2013, mocetinostat has been evaluated in 440 patients in 13 clinical trials (analyses were performed based on 435 patients for whom sufficient information was captured in the database at the time of data cut).

System organ classes (SOCs) with the most frequently reported AEs ( $\geq 20\%$  of all patients for an SOC) across all studies are summarized in Table 3-3; individual events occurring in  $\geq 10\%$  of all patients in a preferred term category within those SOCs are also presented. Overall, the percentage of patients experiencing any AE was 99.3%. The most frequent AEs (occurring in  $\geq 20\%$  of patients in a preferred term category) were nausea (71%), fatigue (70%), diarrhea (57%), vomiting (49%), anorexia (36%), anemia (26%), constipation (25%), pyrexia (25%), thrombocytopenia (24%), decreased weight (23%), abdominal pain (22%), cough (21%), dyspnea (21%), and peripheral edema (20%).

The most frequent AEs (occurring in  $\geq$ 10% of patients in a preferred term category) considered related to study drug were the following: nausea (66%), fatigue (63%), diarrhea (50%), vomiting (44%), anorexia (31%), weight decreased (21%), anemia (21%), thrombocytopenia (20%), neutropenia (16%), abdominal pain (14%), decreased appetite (13%), asthenia (13%), constipation (12%), pyrexia (12%), dyspepsia (12%), headache (11%), dizziness (10%), and peripheral edema (10%).

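### Section 9.3 gives no hold, resume or reduce rule for drug-related hematologic toxicity, and the dose ladder such a rule would use is inconsistent

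*Combined protocol and SAP*

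**What the plan says.** **Section 9.2.** Patients start at 70 mg and go to 90 mg from cycle 2 unless they have had a drug-related toxicity of grade 3 or higher. For reductions, "Mocetinostat dose reduction will be administered at 20 mg below the current dose". At most three reductions are allowed, the minimum dose is 35 mg, and a reduced dose is never raised again. Treatment withheld for 21 or more consecutive days must stop for good. After an interruption that was not for toxicity, "then treatment with the study drug may be resumed at the same dose". The next sentence extends this: "The same applies if the patient experienced an unacceptable toxicity not specifically described in Table 3-3 or Section 9.3", provided that the toxicity has settled to grade 1 or less and nothing else is specified.

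**Table 9-2.** The doses listed are 70, 50 and 35 mg. A footnote adds: "Dose reduction should be based on the worst preceding toxicity".

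**Section 9.3.1 and Table 9-3.** These cover non-hematologic toxicity only. Grade 3 means hold, then resume one level lower, unless routine supportive care can manage the event. For grade 4, "Subjects who experience grade 4 non-hematologic toxicities should have study treatment discontinued", except that where the investigator and sponsor agree that the patient is benefiting, "treatment may be resumed at a lower dose level as described above following recovery". There is also a time limit, again with an exception: "If there is no recovery within 21 day the subject will go off protocol treatment".

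**Sections 9.3.2 to 9.3.5.** These cover gastrointestinal toxicity, cystitis, pericardial toxicity and the work-up of chest pain.

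**Section 3.2.8.** The most frequent adverse events "across all studies are summarized in Table 3-3". This is background, not a dosing table.

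**The concern.** Low blood counts are an expected effect of this drug, and the protocol does not say at what grade to hold it or at what dose to restart. Two other places read as if it did. Section 10.3 orders repeat blood counts when a grade 2 to 4 hematologic toxicity calls for a dose change or interruption. Section 9.4.3 forbids growth factors in place of a scheduled reduction. No hematologic reduction is scheduled anywhere.

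What is at stake is patient safety and consistent dosing. A treating physician could follow every written rule and still keep dosing through a severe cytopenia, and two physicians could treat the same event differently.

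**Working it through.** The plan states no figure on this point, so most of the check sets sections against each other. The arithmetic gives scale and tests the dose ladder.

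1. **Is there a hematologic rule?** Sections 9.3.1 to 9.3.5 and Tables 9-2 to 9-4 give no grade, count, hold or resumption dose for any cytopenia. The subsection and table numbers run without a gap, so a lost subsection is unlikely. Sections 9.4, 10.3, 11 and 13 do not supply one either.

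2. **Does the Section 9.2 default cover cytopenias?** It excludes toxicities described in Table 3-3. Section 3.2.8 gives that table's inclusion rule: organ classes with adverse events in at least 20% of patients and, within them, individual events in at least 10%.
   - Organ class: grade 3/4 blood and lymphatic events alone are 175/435 = 40.2%, above 20%.
   - Anemia is 26% and thrombocytopenia 24%, both above 10%.
   - Neutropenia is 16% counting drug-related events only, so at least 16% overall.
   - Febrile neutropenia is 52/435 = 12.0% at grade 3/4 alone.

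   All four meet the rule. Read literally, they are outside the default, and no other text gives a resumption dose.

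3. **How often would this arise?** Expected count = rate × n, using the pooled drug-related grade 3/4 rates in Section 3.2.8. The two sample sizes are the planned 56, and 20 if both cohorts stop after the first stage.

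| Event | Rate | Of 56 | Of 20 |
|---|---|---|---|
| Neutropenia | 14% | 7.84 | 2.8 |
| Thrombocytopenia | 14% | 7.84 | 2.8 |
| Anemia | 9% | 5.04 | 1.8 |
| Febrile neutropenia | 7% | 3.92 | 1.4 |

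   One patient can have several of these, so the rows do not add. At 14%, the chance of at least one such event among 20 patients is 1 − 0.86^20 = 0.95.

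4. **Does the ladder work?** From 50 mg, the 20 mg rule gives 50 − 20 = 30 mg, below the 35 mg floor, whereas Table 9-2 goes to 35 mg. From 70 mg, the table allows two reductions (70 to 50 to 35). The permitted three exist only from 90 mg (90 to 70 to 50 to 35), and the table omits 90 mg.

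5. **What would each reduction cost?** 20/90 = 22.2%; 20/70 = 28.6%; 15/50 = 30.0% less drug per dose.

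**The case against.** **Other safeguards exist.** Treatment stops for intolerable toxicity, and unacceptable toxicity is a ground for withdrawal. A drug-related event of grade 3 or higher blocks escalation. The 21-day limit applies to any cause. Transfusions are allowed, as are growth factors for severe anemia or neutropenia, and the investigator may withdraw a patient at any time. All of this stands, and a careful investigator may already do what is proposed here. But none of it sets a trigger for holding the drug or a dose for restarting it. The Table 9-2 footnote does not either.

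**Lighter handling of cytopenias may be intended.** Table 9-3 lets a grade 3 event managed by routine supportive care resume without reduction, and Section 11.2.1 does not count admission purely for febrile neutropenia as serious. This is a fair point. The documents do not show that cytopenias must be handled as strictly as non-hematologic events. It is a reason to leave the first grade 3 event to clinical judgement, not to leave the rule unwritten.

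**A stronger reading is tempting.** A reader might infer that the Section 9.2 default lets a patient restart at the same dose after a grade 4 cytopenia, which would be looser than the grade 4 non-hematologic rule. The documents do not support that. It holds only if the reference to Table 3-3 is a misprint for a dosing table such as Table 9-3, and nothing in the text says so. As written, the protocol is silent on the resumption dose. Silence is not permission.

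**The pooled rates may not transfer.** The pool mixes diseases (non-Hodgkin lymphoma is 80 of 435, or 18.4%), doses and combination regimens. The rate here could be lower or higher. Section 3.2.6 reports neutropenia and thrombocytopenia as more frequent in MDS, leukemia or lymphoma than in other cancers. The counts are for scale only.

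**Conclusion.** The gap is real and worth closing before patients are treated. Two points are firm, because they rest on the text and simple subtraction: no hematologic dosing rule exists, and the ladder contradicts itself at its last step.

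The conclusion that cytopenias fall outside the same-dose default rests on the literal citation and on Table 3-3 following its stated inclusion rule. The body of that table is not in the text available here. If the citation were a misprint, the default would cover cytopenias and a rule would be needed all the more.

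On the pooled rates, roughly 4 to 8 of 56 patients would have each type of drug-related grade 3/4 event. No separate grade 4 rate is given, so the number at that grade cannot be stated.

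This is a safety and conduct point. The two-stage response rule in Section 14 and its stated error rates do not change, and the planned toxicity analysis is descriptive.

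**What to change.** 1. **Add a hematologic entry to Section 9.3** that names neutropenia, febrile neutropenia, thrombocytopenia and anemia.
   - Drug-related grade 4: hold until grade 1 or less, or baseline, then resume one dose level lower.
   - Drug-related grade 3, including grade 3 febrile neutropenia: hold to the same criterion. The clinical team decides in advance, and writes down, whether a first event resumes at the same dose.
   - Cite the Section 9.2 limit (21 or more days withheld), because Section 9.3.1 attaches an exception and Section 13.1 counts more than 21 days.

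2. **Restate Table 9-2 as 90, 70, 50 and 35 mg**, and say in Section 9.2 that the last step is 15 mg. This gives exactly the three reductions already allowed.

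Leave the reference to Table 3-3 alone, or change it only once the new entry names every cytopenia. Deleting it first would move any unnamed cytopenia into the same-dose default.

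**Cost.** A short amendment and no extra visits. Affected patients receive 22% to 30% less drug per dose at each step with no re-escalation, which could lower their chance of response. Some with slow count recovery will come off treatment under the 21-day limit.
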